8.1.1.4. Psoriatic Arthritis Disease Activity Score

The Psoriatic Disease Activity Score (PASDAS) is a weighted index comprising the following assessments:

- 68 tender joint count (see [Section 8.1.3.1](#))
- 66 swollen joint count (see [Section 8.1.3.1](#))
- Subject's Global Assessment of Disease Activity (see [Section 8.1.2.2](#))
- Investigator's Global Assessment of Disease Activity (see [Section 8.1.3.2](#))
- 36-Item Short Form Survey (SF-36; see [Section 8.1.2.8](#))
- Leeds Enthesitis Index (see [Section 8.1.3.5](#))
- Leeds Dactylitis Index (see [Section 8.1.3.6](#))
- CRP level in mg/dL.

The score range of the PASDAS is 0 to 10, with worse disease activity represented by higher scores. Change in PASDAS index will be evaluated at Week 16.

8.1.1.5. Minimal Disease Activity and Very Low Disease Activity

The criteria for MDA were developed for rheumatoid arthritis, but a PsA-specific definition of MDA has been constructed (Coates et al, 2010). These criteria were validated and are now considered as a step towards “treatment to target” in PsA, ie, the goal of achieving remission or low disease activity state (Coates et al, 2010; Mease, 2011).

A subject is classified as in MDA when 5 of the following 7 criteria are met (Mease, 2011):

- 68 tender joint count ≤ 1 (see [Section 8.1.3.1](#))
- 66 swollen joint count ≤ 1 (see [Section 8.1.3.1](#))
- PASI ≤ 1 or BSA $\leq 3\%$ (see [Section 8.1.3.3](#))
- Subject’s Pain Assessment (visual analogue scale [VAS]) ≤ 15 mm (see [Section 8.1.2.3](#))
- Subject’s Global Activity VAS ≤ 20 mm (corresponds to Subject’s Global Assessment of Disease Activity, see [Section 8.1.2.2](#))
- HAQ-DI ≤ 0.5 (see [Section 8.1.2.6](#))
- Tender enthesal points ≤ 1 site out of 6 sites included in LEI (see [Section 8.1.3.5](#)).

A subject is classified as in very low disease activity (VLDA) when all 7 criteria described above are met.

The proportion of subjects achieving MDA and VLDA will be evaluated at Week 16.

8.1.2. Patient-reported Outcomes

8.1.2.1. Subject’s Global Impression of Change

Subjects will complete a global impression of change questionnaire at the designated study visits listed in SoA ([Section 1.3](#)).

The questionnaire consists of 1 self-administered item that assesses change in disease activity. Subjects will be asked to indicate their impression of change compared with start of treatment.

8.1.2.2. Subject’s Global Assessment of Disease Activity

Subject’s global health assessment will be evaluated at the designated study visits listed in SoA ([Section 1.3](#)) using a VAS.

The VAS is a horizontal line, 100 mm in length, with anchor statements on the left (0 mm) and on the right (100 mm). The subject will be asked to place a single vertical line through the VAS at the point that best corresponds to their feeling of disease activity.

The score is obtained by measuring the distance from 0 to the line drawn by the subject.

8.1.2.3. Subject’s Assessment of Pain (VAS)

Pain will be assessed by the subject at the designated study visits listed in SoA ([Section 1.3](#)) using a VAS.

The VAS is a horizontal line, 100 mm in length, with anchor statements on the left (0 mm) and on the right (100 mm). The subject will be asked to place a single vertical line through the VAS at the point that best corresponds to their feeling of pain.

The score is obtained by measuring the distance from 0 to the line drawn by the subject.

8.1.2.4. Subject's Assessment of Spinal Pain (NRS)

Spinal pain will be assessed by the subject at the designated study visits listed in SoA ([Section 1.3](#)) using a numeric rating scale (NRS).

The subject will be asked to circle the number between 0 and 10 that fits best to their spinal pain intensity, with “0” indicating “no pain” and 10 indicating “worst imaginable pain”.

8.1.2.5. Widespread Pain Index

The Widespread Pain Index (WPI) is a self-report measure used to assess bodily distribution of pain and to specifically quantify the degree of widespread body pain and assess for centralized pain features. The WPI assesses the presence of pain in 19 designated body locations over the past 7 days (eg, neck, right upper arm, left lower leg). Each location is equal to a score of 1. Items are summed to yield a total score, with higher scores indicating greater widespread pain ([Dudeney et al, 2019](#)).

The WPI will be presented in local language and is to be completed by the subject at the designated study visits listed in SoA ([Section 1.3](#)).

8.1.2.6. Health Assessment Questionnaire – Disability Index

The HAQ-DI questionnaire is a patient-reported outcome that is self-administered by the subject. It covers 8 sections: dressing, arising, eating, walking, hygiene, reach, grip, and activities.

The HAQ-DI will be presented in local language and is to be completed by the subject at the designated study visits listed in SoA ([Section 1.3](#)).

8.1.2.7. Psoriatic Arthritis Impact of Disease

The PsAID is a questionnaire developed by EULAR to assess the subject's physical and psychological domains related to PsA. The questionnaire used in clinical trials consists of 9 questions (PsAID-9; [Gossec et al, 2014](#)).

The PsAID-9 score gives a number between 0 and 10. A higher score on the PsAID-9 indicates more impact of the disease. A score below 4 out of 10 is considered a patient-acceptable status. A change of 3 or more points is considered a relevant absolute change.

The PsAID-9 questionnaire will be presented in local language and is to be completed by the subject at the designated study visits listed in the SoA ([Section 1.3](#)).

The subject should complete the questionnaire before site personnel perform any clinic assessments and before any interaction with the site personnel has occurred to avoid biasing the subject's response.

8.1.2.8. Short Form-36

The acute Short Form-36v2 Health Survey (SF-36) is 36-item questionnaire that measures 8 dimensions related to functioning and well being including physical functioning, role-function, bodily pain, general health, vitality, social functioning, role-emotional, and mental health.

The SF-36 questionnaire will be presented in local language and is to be completed by the subject at the designated study visits listed in the SoA ([Section 1.3](#)).

The subject should complete the questionnaire before site personnel perform any clinic assessments and before any interaction with the site personnel has occurred to avoid biasing the subject's response.

8.1.2.9. Functional Assessment of Chronic Illness Therapy-Fatigue

The FACIT measurement system was originally developed to assess health-related quality of life in subjects with chronic illnesses. The additional questions of the Functional Assessment of Chronic Illness Therapy – Fatigue (FACIT-F) survey were compiled to assess anemia-related fatigue ([Mease, 2011](#)).

The FACIT-F comprises 13 items in total and each item is answered based on a 5-point Likert scale. Responses of “not at all”, “a little bit”, “somewhat”, “quite a bit”, and “very much” are available for each question, and correspond to scores of 0, 1, 2, 3, and 4, respectively.

The FACIT-F questionnaire will be presented in local language and is to be completed by the subject at the designated study visits listed in the SoA ([Section 1.3](#)).

8.1.3. Investigator's Assessments

The following investigator assessments should be performed by an independent and blinded assessor, if available, who should not perform any other study related procedures.

- Psoriasis Area Severity Index (PASI)
- body surface area (BSA)
- TJC and SJC Assessment
- Dactylitis assessments
- Enthesitis assessments
- modified nail psoriasis severity index (mNAPSI)

In order to minimize variability, the same assessor should evaluate the subject at each visit for the duration of the trial. A back-up assessor should be identified. The assessor should be a qualified medical professional (e.g. nurse, physician's assistant, or physician) or be pre-approved by the Medical Monitor or Sponsor as an assessor after review of assessor training and experience. Any assessor must be trained and competent in performing such assessments. It is the responsibility of the Investigator to ensure that all assessors are qualified and trained to perform assessments and that all training is documented. If the assessor is not available, the pre-identified back-up assessor should perform such assessments.

Abbreviations: ACR = American College of Rheumatology; DAPSA = Disease Activity in Psoriatic Arthritis; DAS28 = Disease Activity Score in 28 joint; DIP = distal interphalangeal; L = left; MCP = metacarpophalangeal; MDA = Minimal Disease Activity; MTP = metatarsophalangeal; PASDAS = Psoriatic Disease Activity Score; PIP = proximal interphalangeal; R = right; VLDA = very low disease activity.

8.1.3.2. Investigator's Global Assessment of Disease Activity

Investigator's global health assessment related to subject's disease activity will be evaluated at the designated study visits listed in SoA ([Section 1.3](#)) using VAS.

The VAS is a horizontal line, 100 mm in length, with anchor statements on the left (0 mm) and on the right (100 mm).

The investigator will be asked to place a single vertical line through the VAS at the point that best corresponds to the subject's disease activity.

The score is obtained by measuring the distance from 0 to the line drawn by the investigator.

8.1.3.3. Psoriasis Area and Severity Index and Affected Body Surface Area

Psoriasis Area and Severity Index is an index used to express the severity of psoriasis. Because its performance characteristics are diminished in subjects with low lesional burden, it is not typically calculated in subjects with < 3% BSA involvement with psoriasis lesions ([Mease, 2011](#)).

After start of treatment, PASI will only be assessed if psoriasis affects $\geq 3\%$ of subject's BSA at baseline. The BSA assessment measures the total area of the body affected by psoriasis.

Psoriasis Area and Severity Index evaluates the severity of erythema, induration, and desquamation in 4 body sections (head, arms, trunk, and legs).

Psoriasis Area and Severity Index and affected BSA will be assessed at the designated study visits listed in the SoA ([Section 1.3](#)).

8.1.3.4. Modified Nail Psoriasis Severity Index

The Nail Psoriasis Severity Index is a numeric, reproducible, objective, simple tool for evaluation of nail psoriasis ([Rich and Scher, 2003](#)). Nail bed psoriasis includes onycholysis, splinter hemorrhages, hyperkeratosis, and "oil-drop change", while nail matrix psoriasis includes pitting, leukonychia, lunular red spots, and nail plate crumbling ([Mease, 2011](#)).

A modification of this system, the modified Nail Psoriasis Severity Index (mNAPSI), is a shorter and more feasible scoring system that has demonstrated excellent interrater reliability and has been used in PsA clinical trials ([Mease, 2011; Cassell et al, 2007](#)). For each fingernail, 7 groups of features are evaluated: pitting, onycholysis and oil-drop dyschromia, nail plate crumbling,

leukonychia, splinter hemorrhages, hyperkeratosis, and red spots in the lunula. Pitting, onycholysis and oil-drop dyschromia, and crumbling (including fragmentation and horizontal ridging of the nail bed) are graded from 0 to 3 in severity. Leukonychia, splinter hemorrhages, hyperkeratosis, and red spots in the lunula are graded as either present or absent.

An mNAPSI will be calculated at the designated study visits listed in the SoA ([Section 1.3](#)).

8.1.3.5. Leeds Enthesitis Index and Spondyloarthritis Research Consortium of Canada Enthesitis Index

The LEI and the Spondyloarthritis Research Consortium of Canada (SPARCC) Enthesitis Index are both used to assess enthesitis in subjects with PsA. The LEI assesses 6 enthesal sites, while the SPARCC Enthesitis Index assesses enthesitis at 16 anatomical sites (see Table 5). Tenderness on examination will be recorded as either present (1) or absent (0) for each of the sites, for an overall score range of 0 to 6 (LEI) and 0 to 16 (SPARCC Enthesitis Index). Higher count represents greater enthesitis burden ([Mease, 2011](#)).

The investigator will assess the 16 sites of the SPARCC Enthesitis Index plus 2 sites of the LEI (right and left medial condyle femur; see Table 5) at the designated study visits listed in the SoA ([Section 1.3](#)).

Table 5. Enthesal sites assessed for enthesitis according to SPARCC and LEI

Anatomical sites assessed for tenderness	SPARCC (16 sites)	LEI (6 sites)
Supraspinatus insertion into the greater tuberosity of the humerus	R, L	-
Lateral epicondyle humerus	R, L	R, L
Medial epicondyle humerus	R, L	-
Achilles tendon	R, L	R, L
Greater trochanter	R, L	-
Medial condyle femur	-	R, L
Plantar fascia insertion at the calcaneus	R, L	-
Quadriceps insertion into the superior border of the patella	R, L	-
Patellar tendon insertion at the inferior pole of the patella	R, L	-

Abbreviations: L = left; LEI = Leeds Enthesitis Index; R = right; SPARCC = Spondyloarthritis Research Consortium of Canada.

8.1.3.6. Leeds Dactylitis Index

Using the Leeds Dactylitis Index, one can quantify the size and tenderness of a swollen digit, enabling differentiation between tender and nontender dactylitis. Each of 20 digits (ie, all fingers and toes) will be evaluated for size (circumference close to the base measured in millimeter) and tenderness. For use in clinical trials, circumferences of the affected and contralateral digits are

measured using a measuring tape or a precalibrated loop. The circumference of the affected digits, circumference of contralateral digits, and tenderness of affected fingers are all assessed for a total score. A difference in digital circumference of > or =10% is used to define a finger with dactylitis ([Mease, 2011](#); [Kaeley et al, 2018](#)).

The presence or absence of tenderness at 20 digits and the circumference of each digit will be assessed and documented by the investigator at the designated study visits listed in the SoA ([Section 1.3](#)).

8.1.3.7. Investigator Question on Presence of Axial Involvement

The presence of axial involvement will be recorded at baseline.

Investigator will respond Yes/No to the following question: “*Does the subject have axial involvement?*”.

8.1.3.8. Radiographic Assessment and modified total Sharp score

Radiographs of hands, wrists, and feet will be performed at baseline, Week 16, and Week 52 or EOT in order to evaluate the presence and extent of PsA-related structural damage over the course of the study. Radiograph of the pelvis will be performed at baseline.

Radiographs of hands, wrists, and feet will be performed if subjects discontinue the study drug after Week 16 and it has been at least 12 weeks from the date of last radiographs obtained.

Radiographs should be obtained as close as possible to the last dose of study drug.

Psoriatic arthritis radiographic progression will be measured by the modified total Sharp score (mTSS). The mTSS is a detailed scoring method evaluating erosions, joint space narrowing, (sub)luxation, ankylosis, gross osteolysis, and pencil in cup phenomena. It typically assesses joints of the hands and feet, including the second to fifth distal interphalangeal joints of both hands ([van der Heijde et al, 2005](#)).

The maximum score for erosions is 5 in the joints of the hands and 10 in the joints of the feet. Scores for erosions are as follows: 0 = no erosions; 1 = discrete erosion; 2 = large erosion not passing the midline; 3 = large erosion passing the midline.

A combination of the above scores may lead to a maximum of 5 per entire joint in the hands, and 5 at each site of the joint (for the entire joint a maximum of 10) in the feet. The joint space narrowing score is based on the following features: 0 = normal; 1 = asymmetrical or minimal narrowing up to a maximum of 25%; 2 = definite narrowing with loss of up to 50% of the normal space; 3 = definite narrowing with loss of 50 to 99% of the normal space or subluxation; 4 = absence of a joint space, presumptive evidence of ankylosis, or complete luxation.

Gross osteolysis and pencil in cup are scored separately. In the final summary score, joints with 1 of these abnormalities get the maximum score assigned for both erosions and for joint space narrowing. The maximum possible scores are 320 for erosions, 208 for joint space narrowing, and 528 for the total score.

8.2. Safety Assessments

Planned timepoints for all safety assessments are provided in the SoA ([Section 1.3](#)).

8.2.1. Medical and Medication History

A complete medical and medication history, as well as history of alcohol and nicotine use, will be obtained from each subject during the screening visit. An updated medical history will be obtained at the Day 1 visit prior to study drug administration and updated as necessary throughout the study.

A PsA history obtained at screening will capture date of onset of PsA and psoriasis (if applicable).

Any systemic treatment for plaque psoriasis and PsA (ie, DMARDs, biologics, steroids) since diagnosis will be recorded. Any other treatment used for any other reasons (including contraception) prior to randomization will be recorded as per eCRF Completion Guidelines.

Any changes in concomitant medication will be recorded throughout the study, from Day 1 until End of Study at Week 65.

8.2.2. Physical Examination

A complete physical examination will include, at a minimum, assessments of the dermatological, cardiovascular, respiratory, gastrointestinal, and neurological systems.

Clinically significant findings observed prior to first dose of study drug should be listed as medical history in the eCRF and reported as AEs if observed after first dose of study drug.

8.2.3. Physical Measurements

Height and weight measurements are to be performed at the designated study visits listed in the SoA ([Section 1.3](#)) and data will be recorded in cm and kg, respectively. Height and weight are to be measured without shoes.

8.2.4. Vital Signs

Vital signs will be measured in a sitting position after 5 minutes' rest and will include temperature, systolic and diastolic blood pressure, and pulse and respiratory rate.

8.2.5. Electrocardiograms

TriPLICATE 12-lead ECGs will be obtained one minute apart after subject has been supine for at least 5 minutes as outlined in the SoA ([Section 1.3](#)) using an ECG machine that automatically calculates the heart rate and measures PR, QRS, QT, intervals.

8.2.6. Chest X-ray

Chest x-ray (posterior/anterior or anterior/posterior) in addition to the TB blood test will be performed at screening in subjects who do not have a chest x-ray available within 3 months of screening. A subject must not be included in the study if his/her chest x-ray reveals evidence of active TB or fungal infection (refer to [Section 5.2](#)). Women of childbearing potential must have a negative pregnancy test before an x-ray is performed.

8.2.7. Hospital Anxiety and Depression Scale

Depression and anxiety will be monitored with the Hospital Anxiety and Depression scale (HADS). The HADS was chosen for its well-established psychometric properties and its use in clinical research on biological therapy in subjects with other inflammatory skin diseases (Langley et al, 2010). The HADS scores for anxiety and for depression range from 0 to 21 with higher scores indicating a worse state. A score < 8 is considered to be normal, whereas a score of ≥ 11 is considered clinically significant (Snaith, 2003).

The HADS questionnaire will be presented in local language and is to be completed by the subject at the designated study visits listed in the SoA (Section 1.3).

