- Progression of structural damage assessed radiographically and expressed as the change in mTSS at Weeks 16 and 52, compared to baseline
- Change in SPARCC enthesitis score at Weeks 16, 24, and 52, as compared to baseline in subpopulation with enthesitis (SPARCC  $>0$ ) at baseline

- Change in spinal pain NRS at Weeks 16, 24, and 52, as compared to baseline in subjects reporting spinal pain at baseline
- Change from baseline in spine pain NRS in those with sacroiliitis on pelvic x-ray at Weeks 16, 24 and 52
- Change from baseline in spine pain NRS in those with investigator assessed spinal involvement at Weeks 16, 24 and 52
- Association of investigator assessed sacroiliac involvement with sacroiliitis on x-ray
- Proportion of subjects achieving each MDA component (TJC68, SJC66, PASI, BSA, SAPVAS, SGADA, HAQ-DI, tender enthesal points from LEI) at Weeks 16, 24 and 56
- Change in quality of life as assessed by SF-36 total score, physical component summary (PCS), and mental component summary (MCS) change from baseline to Weeks 16, 24, and 52
- Fatigue as assessed by FACIT-F change from baseline to Weeks 16, 24, and 52
- Proportion of subjects achieving ACR50 at Weeks 24 and 52
- Proportion of subjects with resolution of enthesitis at Weeks 24 and 52 as assessed by LEI in subpopulation that had enthesitis (LEI > 0) at baseline
- Proportion of subjects achieving an improvement in PsAID of at least 3 units at Weeks 24 and 52 compared to baseline in subjects with PsAID  $\geq 3$  at baseline
- Proportion of subjects achieving ACR20 at Weeks 24 and 52
- Mean (median) ACR-N at Week 16, where, ACR-N is defined as the largest number N such that ACR-N is met (analogous to the primary endpoint definition of ACR 50)
- Change in enthesitis at Weeks 16, 24 and 52 as assessed by change from baseline in LEI
- Time to resolution of enthesitis at weeks 4, 12 and 16 among subjects with enthesitis (LEI > 0) at baseline
- Occurrence of enthesitis (LEI > 0) at weeks 4, 12 and 16 among subjects without enthesitis (LEI = 0) at baseline
- Depression and anxiety as assessed by change in HADS score from baseline to Weeks 16 and 52
- Change in physical function as assessed by HAQ-DI change from baseline to Weeks 24 and 52
- Proportion of subjects with a decrease of at least 2 from baseline in LEI, among subjects with baseline LEI of at least 2, at weeks 4, 12 and 16
- Subject's Global Impression of Change Questionnaire at weeks 16 and 52

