- Change from baseline in LEI at Week 16, 24, 52
- Time to resolution of enthesitis at weeks 4, 12 and 16 among subjects with enthesitis (LEI > 0) at baseline
- Occurrence of enthesitis (LEI > 0) at week 4, 12 and 16 among subjects without enthesitis (LEI = 0) at baseline
- HADS change from baseline to Weeks 16 and 52
- Decrease of at least 2 from baseline in LEI, among subjects with baseline LEI of at least 2, at weeks 4, 12 and 16
- Subject's Global Impression of Change Questionnaire at weeks 16 and 52
- AUC for ACR-N through week 16
- Time to first achievement of ACR50
- Time to first achievement of PASI90 among subjects with at least 3% BSA at baseline
- Time to first achievement of MDA
- Time to first achievement of ACR20
- Time to first achievement of PsAID improvement of at least 3 among subjects with PsAID at least 3 at baseline
- Time to first achievement of PASI100 among subjects with at least 3% BSA at baseline
- Trough plasma concentrations of izokibep at collected timepoints
- Presence of anti-drug antibodies (positive or negative)

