#### **2.7.6. Hospital Anxiety and Depression Scale**

Depression and anxiety will be monitored with the Hospital Anxiety and Depression scale (HADS). The HADS questionnaire will be completed by the subject.

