For comparisons of izokibep to placebo, the three dosing regimens of izokibep (QW, Q2W and Q4W) will be compared separately to placebo. Binary endpoints including the primary endpoint of ACR50 will be compared with a stratified test of risk difference. Continuous endpoints will be compared with a repeated measures mixed model.

Safety data, such as adverse events, serious adverse events, and laboratory data, will be summarized.

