- ACR70 at Weeks 16, 24, and 52
- DAPSA  $\leq 14$  at Weeks 16, 24, and 52
- cDAPSA  $\leq 14$  at Weeks 16, 24, and 52
- DAPSA  $\leq 4$  at Weeks 16, 24, and 52
- cDAPSA  $\leq 4$  at Weeks 16, 24, and 52
- PASI75 at Weeks 16, 24, and 52
- PASI100 at Weeks 16, 24, and 52
- MDA at Weeks 24, and 52
- VLDA at Weeks 16, 24, and 52
- Resolution of dactylitis at Weeks 16, 24, and 52 among those with dactylitis at baseline
- ACR50 at Weeks 24 and 52
- PASI90 at Weeks 24 and 52 among those with  $\geq 3\%$  BSA psoriasis at baseline
- Resolution of enthesitis (LEI = 0) at Weeks 24 and 52 among those with LEI  $> 0$  at baseline
- Resolution of enthesitis (SPARCC = 0) at Weeks 24 and 52 among those with SPARCC  $> 0$  at baseline
- PsAID response at Weeks 24 and 52
- ACR20 at Weeks 24 and 52
- Occurrence of enthesitis (LEI  $> 0$ ) at weeks 4, 8, 12 and 16, among subjects with no enthesitis (LEI = 0) at baseline
- Decrease of at least 2 in LEI, among subjects with baseline LEI of at least 2, at weeks 4, 8, 12 and 16.

The following continuous endpoints will be analyzed at week 16 with an MMRM model as specified in sec 6.6.3, and after week 16 with standard summary statistics for continuous endpoints. LS mean changes and associated SEs with associated 95% CI and p-values will be presented. Models through week 16 will include all data up to Week 16. The following continuous endpoints after Week 16 will be analyzed according to the four randomized treatment groups. Mean changes and associated SEs along with 95% CI according to the four randomized treatment groups will be presented without strata. No p-values will be reported.

- Change from baseline in DAS28-CRP at Weeks 16, 24, and 52
- Change from baseline in DAPSA/cDAPSA at Weeks 16, 24, and 52
- Change from baseline in PASDAS at Weeks 16, 24, and 52

- Change from baseline in mNAPSI at Weeks 16, 24, and 52 in those with nail psoriasis at baseline
- Change from baseline in mTSS at Weeks 16 and 52
- Change from baseline in SPARCC enthesitis score at Weeks 16, 24, and 52 in those with enthesitis at baseline (SPARCC>0)
- Change from baseline in spinal pain NRS at Weeks 16, 24, and 52
- Change from baseline in spine pain NRS in those with sacroiliitis on pelvic x-ray
- Change from baseline in spine pain NRS in those with investigator assessed spinal involvement
- Correlation of investigator assessed spinal involvement with sacroiliitis on x-ray

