- Change from baseline in SF-36 total score, PCS, and MCS at Weeks 16, 24, and 52
- Change from baseline in FACIT-F at Weeks 16, 24, and 52
- Change from baseline in LEI enthesitis score at Weeks 16, 24, and 52 in those with enthesitis at baseline (LEI>0)
- HAQ-DI change from baseline to Weeks 24 and 52
- HADS change from baseline to Week 24 and 52

Change from baseline for the individual components of the ACR and MDA scores will be summarized at Week 16. Summary statistics (n, mean, standard deviation, median, minimum, and maximum) will be provided

- Swollen Joint Count
- Tender Joint Count
- SAPVAS
- SGADA
- IGADA
- HAQ-DI
- CRP
- PASI
- BSA
- Tender enthesal points  $\leq$  1 site out of 6 sites included in LEI

The following will be analyzed with a time to event model, using a log rank test with stratification by the factors used to stratify randomization. Subjects who do not achieve the endpoint at or before the week 16 visit will be censored at the time of the last assessment could be derived at or before week 16.

- Time to resolution of enthesitis (LEI = 0) among subjects with enthesitis (LEI = 0) at baseline.
- Time to first achievement of ACR50

- Time to first achievement of PASI90 among subjects with  $\geq 3\%$  BSA psoriasis at baseline
- Time to first achievement of MDA
- Time to first achievement of ACR20
- Time to first achievement of PsAID improvement of at least 3 among subjects with PsAID  $\geq 3$  at baseline
- Time to first achievement of PASI100 among subjects with PsAID  $\geq 3$  at baseline

WPI will be calculated at baseline. WPI is a scale of 0-19, and is a count of how many of 19 body sites the subject reports pain or tenderness in the prior 7 days. Standard summary statistics for binary data will be calculated by baseline WPI (WPI  $\geq 7$  vs.  $< 7$ ) for the following endpoints:

- ACR50 at week 16 (observed responder, observed non-responder, missing)
- LEI responders at week 16 (observed responder, observed non-responder, missing)
- PsAID at week 16 (observed responder, observed non-responder, missing)
- HAQ-DI at week 16: improvement of at least 0.35 (observed responder, observed non-responder, missing)

Area under the curve (AUC) for ACR-N will be calculated for each subject by triangulating the observed values at baseline (by definition ACR-N = 0 at baseline) and weeks 2, 4, 12 and 16. The area for consecutive visits, using nominal time from Week t and Week u, will be calculated as

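### HADS is a declared safety variable with two scores and stated cut-offs, but the SAP gives it no safety analysis or scoring rule, and its analysis list names a week at which HADS is not collected

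*Protocol*

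**What the plan says.** **Status and scoring.** Protocol 8.2.7 sits under Safety Assessments (8.2). It defines the instrument as two scores: "The HADS scores for anxiety and for depression range from 0 to 21 with higher scores indicating a worse state". It then gives thresholds: "A score < 8 is considered to be normal, whereas a score of ≥ 11 is considered clinically significant". SAP 2.7.6, under Safety Variables, repeats that HADS is used to monitor depression and anxiety.

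**Objective and variable.** SAP 2.2.3 has the exploratory objective "Depression and anxiety as assessed by change in HADS score from baseline to Weeks 16 and 52", and SAP 2.6 the variable "HADS change from baseline to Weeks 16 and 52". Protocol Section 3 names the same two weeks.

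**Analysis.** The list of continuous endpoints in SAP 6.6.5 has "HADS change from baseline to Week 24 and 52". For that list, up to Week 16, "LS mean changes and associated SEs with associated 95% CI and p-values will be presented". After Week 16 the SAP plans mean changes with standard errors and confidence intervals by randomized group, with no p-values. SAP 6.4.2 lists HADS once, as a continuous baseline characteristic.

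**Collection.** The Schedule of Activities (Protocol 1.3) marks HADS at Day 1, Week 16 and end of treatment, and nowhere else.

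**The concern.** A measure declared as safety monitoring, with a published threshold quoted in the protocol, would normally be reported as the number of subjects in each arm who cross that threshold. The plan never asks for this. A mean change answers a different question: how the average subject moved, not how many entered the range that the protocol calls clinically significant.

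The protocol makes suicidal ideation an event of special interest, so mood is a domain that the sponsor has chosen to watch. HADS is the one instrument in the trial dedicated to anxiety and depression and given clinical cut-offs for them. As the SAP stands, those cut-offs play no part in any analysis. The analysis list also points at a week with no HADS data.

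**Working it through.** The plan states no figure on this point, so there is none to reproduce. The check compares what is declared with what is analysed.

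**1. Is there a safety analysis?** SAP 6.7 covers exposure, adverse events, laboratory data (with a liver review), vital signs, ECG and physical examination, and closes with data monitoring. HADS is absent. Protocol 9.3.5 names exposure, adverse events and laboratory data, and not HADS. Among the measures listed under Safety Variables in SAP 2.7.1 to 2.7.6, HADS is the only one with no counterpart in SAP 6.7.

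**2. Is the scoring defined?** SAP Appendix 2 runs from HAQ-DI (2.1) to MDA and VLDA (2.11) and has no HADS entry. SAP 2.2.3, 2.6, 6.4.2 and 6.6.5 each refer to HADS without saying whether one score or two is meant.

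**3. Does the scoring gap matter for the cut-offs?** The cut-offs apply to each 0–21 score. If a programmer summed the two, the range would be 0 to 21 + 21 = 42, and the cut-offs could not be recovered:

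- Both scores normal: the maximum total is 7 + 7 = 14.
- One score clinically significant: the minimum total is 11 + 0 = 11.
- So totals of 11 to 14 fit either case.
- Neither score at 11 or more: the maximum total is 10 + 10 = 20. So totals of 11 to 20 occur with or without a clinically significant score.

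This is conditional. Neither document says that the scores are summed.

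**4. Which weeks?**

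| Source | Post-baseline HADS timepoints |
|---|---|
| Protocol 1.3, Schedule of Activities | Week 16, end of treatment (Week 52) |
| Protocol Section 3; SAP 2.2.3; SAP 2.6 | Weeks 16 and 52 |
| SAP 6.6.5, analysis list | Weeks 24 and 52 |

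Under SAP 5.1.3, Period 1 ends when the Week 16 assessments are done, before the Week 16 dose. From that dose the placebo group receives izokibep. Week 16 is therefore the only scheduled post-baseline HADS with a concurrent placebo arm. Taken literally, the 6.6.5 list leaves one analysable timepoint, Week 52, when no group is on placebo.

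**The case against.** **Adverse event tables already cover mood.** Partly true. Protocol 10.3.1 makes a worsened safety assessment an adverse event if the investigator judges it clinically significant. SAP 6.7.2 tabulates treatment-emergent events by system organ class and preferred term, and suicidal ideation has its own summary. A reader might infer that new anxiety or depression goes unreported altogether. The documents do not support that. What stands is narrower. Protocol 8.2.7, unlike 8.2.2 (physical findings) and 8.2.8 (laboratory results), gives no instruction to record an abnormal score as an event, and Protocol 8.3.2 prefers open-ended questioning. The adverse event route therefore depends on judgement and is not a count of scores of 11 or more.

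**Other instruments measure mood.** Also true. SF-36 has mental health items and a mental component summary analysed at Week 16, and PsAID-9 has an anxiety item. It would be wrong to infer that HADS is the only systematic mood measurement. The plan attaches no anxiety or depression cut-off to either of the others.

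**The plan gives more than a mean.** Protocol 9.3.1 promises quartiles, median and extremes for continuous data, and SAP 6.6.5 promises efficacy listings. These show something of the tails, but none gives the number above a threshold by arm.

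**No shift table was promised, and the table shells might supply one.** The protocol's HADS objective is a change score, the cut-offs describe the instrument, and the shells are not among the documents. SAP 6.1 says "Safety data, such as adverse events, serious adverse events, and laboratory data, will be summarized", which gives examples and so does not exclude HADS. It does not specify any HADS analysis either.

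**Week 24 is a slip.** Probably, since SAP 2.6 keeps Week 16. It still has to be corrected, because 6.6.5 is the section a programmer works from.

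**Conclusion.** The point holds as a gap in safety reporting. HADS is a declared safety variable with two scores and stated cut-offs, but the SAP gives it no safety analysis and no scoring rule, and does not name the subscales. Questionnaire-defined cases (a new score of 11 or more) are not counted by arm. Separately, SAP 6.6.5 contradicts the objective, the variable and the schedule on timing, and omits the only placebo-controlled HADS visit.

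The size is modest. HADS is an exploratory endpoint, so the primary, secondary and alpha-controlled conclusions are untouched. The documents give no baseline distribution, no standard deviation of change and no expected rate of scores of 11 or more, so the number of cases affected cannot be estimated.

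Two stronger inferences should be resisted. One is that the plan analyses a summed total: it leaves the scoring open. The other is that a mean change would demonstrably hide an excess of worsened subjects. That depends on the distribution of change, which the documents do not give. The case for the count is that it answers the safety question directly, not that the mean has been shown to fail.

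The conclusion assumes that the unseen table shells do not already split the scale and apply the cut-offs.

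**What to change.** 1. **SAP 6.7:** for the Safety Analysis Set, by arm and period, add for HADS-Anxiety and HADS-Depression separately:
   - a shift table across below 8, 8–10, and 11 or more. The middle band is what lies between the two protocol cut-offs;
   - the number and percentage with a new score of 11 or more, among those below 11 at the reference visit, at Week 16 and at Week 52/end of treatment.

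   For the placebo-to-izokibep group, use Week 16 as the Period 2 reference. State which period an early end-of-treatment questionnaire belongs to.
2. **SAP 2.6, 6.4.2 and 6.6.5:** name the two subscale scores in place of HADS.
3. **SAP Appendix 2:** add HADS scoring, including the handling of missing items.
4. **SAP 6.6.5:** change Week 24 to Week 16 for HADS.

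The formats already exist in this SAP: category shift tables for laboratory data (6.7.3) and a separate Period 2 baseline in the Hy's Law tables (6.7.3.1). No new assessment is needed. The cost is a few extra descriptive tables, some with small counts, especially in the 25-subject Q4W arm. They should carry no p-values, in line with Protocol 9.3.5.
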